Osteoarthritis affects 40 million Americans and 15 million people in the United States suffer from degenerative arthritis of the knee. Unicondylar knee arthroplasty (UKA) was introduced as a treatment option for degenerative arthritis of the knee in the early 1970's[1]. The procedure initially yielded variable results and this unpredictability resulted in broadly low levels of usage[1]. Recent improvements in the surgical techniques and technology used for UKA have increased the effectiveness of this surgery. As the average age of the United States population increases, this surgical procedure will become even more common. It is estimated by the Millennium Research Group that there will be 55,100 unicompartmental knee procedures in 2010 and the compound annual growth rate from 2009 to 2014 will be 8.3%.

UKA can be viewed as an attractive alternative to total knee arthroplasty (TKA) assuming the patient's osteoarthritis has remained isolated in a single compartment. UKA is generally a less invasive procedure than TKA. Since the procedure is less invasive there is usually less blood loss; more cartilage, tissue, and bone is spared, which results in shorter recovery times than TKA. This procedure is attractive to adults who are interested in remaining active pain-free lifestyles as they age.

Medical Need:

The cost-effectiveness of healthcare interventions, especially new technology, is becoming essential. Comparing the procedural costs of robotic-assisted surgery and the outcomes of the patients versus TKA, the gold standard, will help substantiate whether robotic-assisted surgery from an economic

viewpoint is a cost-effective treatment. In addition the rehabilitation after knee replacement surgery is critical to achieving proper functional outcomes. Information pertaining to knee replacement post discharge costs has been limited. Due to the lack of studies and the continued growth in the number of knee arthroplasty surgeries it is imperative to track post discharge costs of all variables.

Specific Aim:

To document and compare the procedural and postoperative costs, recovery time, and outcomes of two procedure types:

- Robotic assisted unicompartmental knee arthroplasty
- Manual total knee arthroplasty

Methods Overview:

Objectives:

To quantify the procedural costs and clinical outcomes of knee replacement surgery.

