- Patients will be given a functional test by a physical therapist preoperatively to get an initial starting point. The physical therapist will create a regimen for the patient to complete post operatively with an end point that is reachable based on the starting point. The length of time associated with reaching the end point will be captured.
- Patient employment will be documented. In addition a patient's leave from work will be recorded which may include things such as; short-term disability, vacation, or unpaid leave from work. The patient's salary will be requested and used to track the cost of missed time. If a patient elects not to disclose salary his or her zip code will be requested in order to find the median salary per that area. Worker's compensation claims may or may not factor into rehabilitation adherence and recovery time and will therefore be excluded from this study.
- A patient's return to work and function at work will be logged. The information will be compared based on procedure type.
- The time it takes a patient to return to driving will be tracked. In addition if the knee replacement procedure was performed on the left leg or right leg will be documented because this could factor into time it takes to return to driving. The length of time to return to driving will be reported by procedure type.
- The procedural costs of the different type of knee replacement allocated into different cost centers. The charges, costs, and reimbursements will also be examined and the data be gathered from the hospital accounting software.

Inclusion Criteria:

Study Design Patients will be recruited into the study under the direction of one of the principal investigators or qualified team members during regularly scheduled clinic visits. All patients over 21 years of age who require knee replacement surgery will be asked to participate in the study. These patients will have failed non-operative management of their joint disease and are candidates for partial joint replacement because of pain and joint stiffness that interferes with their performance of normal daily activities.

- Age, 21-80 years
- Sex, males and females will be included
- BMI less than or equal to 39
- Stable health, the patient would be able to undergo surgery and participate in the follow-up program based on physical examination and medical history
- Patient is willing and able to cooperate in follow-up therapy at Rebound facilities

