The study investigator will evaluate the patients for study inclusion/exclusion at their perioperative consultation visit. The surgeon will describe the various surgical options that he believes to be appropriate for each individual patient. The patient and surgeon then will determine which prosthesis is most appropriate for their surgical procedure. Then the surgeon or his assistant will explain the study to the prospective participant. Prospective participants will be encouraged to ask questions regarding study participation. Once they are fully informed about the study, the interested patients will be asked to sign a consent form.

Evaluation to be used for Knee Replacement Patients:

At each clinic visit which coincides with a study interval (preoperative, 2 weeks postoperative, 6 weeks, 3 months, 6 months and 1 Year) the surgeon or qualified member of the study will

- Assess the function and range of motion of the knee joint
- Document any complications that may have occurred after surgery
- Complete a radiographic assessment of the operated knee post-operatively per surgeon standard of care.
- Complete the Knee Society Score in order to provide a rating of the pain, function, range of motion, and knee joint stability for each patient
- Study participants will be asked to complete standardized health-related quality of life instruments to document their perception of their pain and function. Study participants will complete the following outcome instruments. These instruments can be completed via phone, mail, website, or email if a clinic visit is not required at the study interval per surgeon standard of care.
 - a) The American Knee Society Score is subdivided into a knee score that rates only the knee joint itself and a functional score that rates the patient's ability to walk and climb stairs[2].
 - b) The EQ-5D is a standardized instrument for use as a measure of health outcome. Patients will be also given a questionnaire with questions pertaining to employment, loss of wages, driving, etc.
 - c) The Reduced WOMAC is a truncated version of the Western Ontario and McMasters University Osteoarthritis Index. The questionnaire is patient administered and designed to assess pain, disability and joint stiffness in the OA patient[3].

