Financial data will be obtained from each facilities cost accounting system. If data cannot be attained using this method, CPT codes will be recorded and cross-referenced with the 2010 Medicare Fee Schedule. The financial data will be estimated using this method. The use of Medicare reimbursement rate is reasonable given that more than 60% of arthroplasty cases are reimbursed by this agency. A patient's analgesic use will be recorded by the surgeon and the Average Wholesale Price will be assigned to each script. Discharge data collected in this study will be compared to 2006 National Hospital Discharge Survey (NHDS).

Data Management:

All data will be collected using data collection forms or questionnaires in clinic or via phone, mail, website or email. The data dependent upon the questionnaire or form will be recorded by the patient, investigator, or qualified team member. Information will then be entered into a secure online data entry system by a qualified team member and the data will be stored in a secure database. Numerous business rules ensure that only properly formatted data is submitted. The information undergoes further verification by a human operator, who checks the integrity of each record prior to submitting it to the database. All access to the information- including reports, queries and data tools- is password protected and restricted to users that have the proper credentials. Information pertaining to cost data will be uploaded separately into the database.

Data Analysis:

Descriptive statistics consisting of frequency tables and percent for categorical variables and means, standard deviations, and ranges for continuous variables will be tabulated at the conclusion of the study.

General Statistical Considerations:

Tabulation of summary statistics, graphical presentations, and statistical analyses will be performed using SAS® software. The primary presentations and analyses will be based on data pooled across study centers. Relevant summaries for individual centers, or combinations of centers, may be presented for primary data. All patient data will be presented in separate data listings. All patients who are enrolled in this study and receive any of the treatments as part of this study will be included in the safety analysis. All testing and confidence intervals will use a 0.05 significance level. All testing is two sided unless otherwise noted.

Patient Characteristics:

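### Missed-work cost at own salary lets a wage difference between the groups appear as, or hide, a procedure difference, and the area-median substitute can bias mean cost in either direction

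*Combined protocol and SAP*

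**What the plan says.** All references are to the combined protocol and SAP.

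- **Endpoints, quantity.** On employment, "a patient's leave from work will be recorded which may include things such as; short-term disability, vacation, or unpaid leave from work".
- **Endpoints, price.** "The patient's salary will be requested and used to track the cost of missed time". Where salary is withheld, "his or her zip code will be requested in order to find the median salary per that area". Zip code is requested only in that case. The plan does not say which median is meant (all workers, full-time workers, a given age band).
- **Study Enrollment Procedure.** Allocation is by choice: "The patient and surgeon then will determine which prosthesis is most appropriate for their surgical procedure".
- **Specific Aim.** "To document and compare the procedural and postoperative costs, recovery time, and outcomes of two procedure types". The Endpoints item on return to work, which follows the salary item, adds "The information will be compared based on procedure type".
- **Data Analysis.** Summaries are "means, standard deviations, and ranges for continuous variables".
- **General Statistical Considerations and Patient Characteristics.** Testing is two-sided at 0.05, and homogeneity testing is mentioned without detail. No adjustment model, alternative wage valuation or sensitivity analysis is given. Salary and occupation are not among the listed baseline summaries.

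**The concern.** Missed-work cost is days off multiplied by a wage, and the wage is specific to the patient. Two patients with the same leave then have different costs. In a randomised trial, wages would be balanced on average. Here the patient and surgeon choose the procedure, so mean wages may differ between groups, and nothing in the analysis separates that difference from recovery time. Because salary is not a listed baseline summary, a reader of the results might not see the imbalance.

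The substitute for an undisclosed salary raises a second, separate issue. Costs are to be summarised by means, but the substitute is a median. In a right-skewed distribution the median lies below the mean. Every non-discloser in an area also receives the same value, so the wage spread within the area is lost for those patients.

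At stake is the interpretation of the missed-work cost figure: whether it reflects how long patients were off work, how much they earn, or who chose to disclose.

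**Working it through.** The documents give no wage, salary spread, non-disclosure rate or sample size, so there is no stated figure to reproduce. All numerical inputs below are assumptions. Days off are taken as independent of wage.

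**1. Wage mix under own-salary valuation.** Mean cost = mean days × mean wage. At equal days and full disclosure, the cost ratio equals the wage ratio:
- wage ratio 1.1, 1.2, 1.3, 1.5 gives an apparent cost difference of 10%, 20%, 30%, 50%.

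The same mechanism can hide a real difference. Suppose one group has 24 days at $250 and the other 30 days at $200:
- own salary: 24 × 250 = $6,000 and 30 × 200 = $6,000, no difference;
- common wage of $200: 24 × 200 = $4,800 against $6,000, a 20% reduction, which matches the reduction in days.

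**2. Median put into a mean.** For lognormal wages with log-SD s, median/mean = exp(−s²/2): 0.923 at s = 0.4, 0.835 at s = 0.6, 0.726 at s = 0.8. If a share q do not disclose and their wages follow the area distribution, relative bias in mean cost = −q × (1 − exp(−s²/2)):
- low end: 0.20 × 0.077 = 1.5% understatement;
- high end: 0.50 × 0.274 = 13.7% understatement.

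**3. Direction.** Let non-disclosers' true mean wage be m times the area mean, with disclosers at the area mean. Relative bias = q(exp(−s²/2) − m) / ((1 − q) + qm). At q = 0.30 and s = 0.6:

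| m | Bias in mean cost |
|---|---|
| 0.6 | +8.0% |
| 0.8 | +1.1% |
| 1.0 | −4.9% |
| 1.2 | −10.3% |
| 1.5 | −17.3% |

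The sign changes where m equals the median/mean ratio, that is, where non-disclosers earn on average exactly the area median.

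**4. Effect of the substitution on the procedure contrast.**
- Same wages and days, 30% non-disclosure in both groups: 0% spurious relative difference.
- Same wages and days, non-disclosure 10% against 30%: (1 − 0.3 × 0.077)/(1 − 0.1 × 0.077) − 1 = −1.5% at s = 0.4, and (1 − 0.3 × 0.274)/(1 − 0.1 × 0.274) − 1 = −5.6% at s = 0.8.
- Wage ratio 1.2, equal days, 30% in each group given the same area median, s = 0.6: (0.7 × 1.2 + 0.3 × 0.835)/(0.7 + 0.3 × 0.835) − 1 = 14.7%. The substitution here dilutes the 20% wage effect.

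**The case against.** The strongest reply has four parts.

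- **Own-salary valuation is a legitimate choice.** It measures the earnings-valued loss these patients had, and a common wage answers a different question. This stands. It is a reason to add a common-wage valuation beside the planned one, and not to call the planned one an error.
- **Imbalance from chosen procedures affects every endpoint.** True. But in this cost the wage enters as a direct multiplier, and a second valuation separates it from recovery time.
- **The scope is small.** Missed work is not in the Endpoints list of what makes up total cost (pain medication, therapy, equipment and follow-up visits). The salary item does not itself state a comparison by procedure; that is inferred from the Specific Aim and the neighbouring return-to-work item. Time to return to work is already a comparative objective, in time units, and salary does not touch it. All of this stands and limits the point to missed-work cost.
- **The inputs are assumed.** Also true.

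A reader might infer that the median rule biases mean cost downward. The documents do not support a direction. A downward bias needs non-disclosers who earn on average more than the area median, as they would if they resembled a right-skewed area distribution. The plan has no data on this, and eligibility runs to age 80, so part-time or near-retirement earners are possible. A reader might also infer that the median rule by itself creates a procedure difference. With equal wages, days and disclosure in the two groups it does not.

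**Conclusion.** The point holds for missed-work cost only, as a minor improvement to the plan.

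The firmer part is wage mix. With own-salary valuation, chosen procedures and no planned adjustment, any difference in mean wage passes into the cost comparison. A ratio of 1.2 gives 20% at equal days off and full disclosure. Whether wages will differ between the groups is not known from the documents.

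The second part is a bias of unknown direction in mean cost. It is about 1.5% to 14% downward if non-disclosers resemble a lognormal area distribution with log-SD 0.4 to 0.8 and 20% to 50% do not disclose; it is upward if they earn on average less than the area median. The substitution also removes within-area wage spread among non-disclosers. The effect on the overall SD was not sized, since days off and differences between areas still vary. The substitution alters the relative procedure contrast only if disclosure or wages differ by group.

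It would go too far to say that the plan's total cost or its return-to-work comparison is compromised: the first does not list missed work, and the second uses no salary.

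**What to change.** - Report work days missed by procedure beside the missed-work cost.
- Add a valuation of those days at one common mean wage for both groups, next to the own-salary valuation. The common-wage result shows recovery time; the gap between the two shows wage mix.
- In the own-salary valuation, replace the bare median with multiple imputation from the disclosed salaries, using age, sex and employment. Add area wage as a predictor only if zip code is requested from all patients: as planned, disclosers have none, so the model could not be fitted with it. If area wage is used, define it.
- Report the non-disclosure rate by group.

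The cost is two valuations to report and some extra analysis, plus one extra data field if area wage is used. The imputation still assumes that disclosure is unrelated to salary given the predictors, and the report should say so. The common-wage valuation needs no individual salary and so avoids that assumption.

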- Patient has stable and functional collateral ligaments
- Patient or patient's legal representative has signed the Informed Consent form
- Failed non-operative management of their joint disease
- Need to obtain pain relief and improved function
- Moderate or severe pain with either walking or at rest
- Diagnosed with osteoarthritis in one or more compartments of the knee and non-surgical treatment options have failed to provide relief for symptoms

- Patient exhibits preoperative radiographic evidence of joint degeneration that cannot be treated in non-operative fashion

Exclusion Criteria:

Patients will be excluded from study participation if they are cognitively unable to complete study health-related quality of life forms and pregnant women are also excluded from participation in this study.

- Patients who, in the opinion of the Investigator, have an existing condition that would compromise their participation and follow-up in the study
- Patients with pre-op flexion contracture greater than 10 degrees, overall flexion less than 115 degrees, and varus/valgus greater than 10 degrees
- Patient who is on workmen's compensation
- Patients who are on chronic long acting preoperative narcotic pain medication
- Patients with inflammatory polyarthritis
- Women who are pregnant
- Subjects who are known drug or alcohol abusers or with psychological disorders that could affect follow-up care or treatment outcomes
- Subjects who are currently involved in another clinical study with the exception to an outcomes study
- Patients with a pathology which, in the opinion of the Principal Investigator, will adversely affect healing
- A diagnosed systemic disease that would affect their welfare or the overall outcome of study (i.e. Paget's disease, renal osteodystrophy)
- Patients receiving an isolated patellofemoral UKA, lateral UKA, or bi-compartmental arthroplasty
- Patients with significant medical condition preventing a well-functioning contralateral knee

Risk/Benefits:

This is a minimal risk study which involves collection of data. The purpose of this study is for research purposes only. There is no direct benefit to the patient to participate in this study. The results of this research study may contribute to clinical research overall and may be published.

Study Enrollment Procedure:

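### Reimbursement is examined by type of knee replacement with no plan to extract payer or hold it constant, so pooled figures could reflect payer mix as well as procedure

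*Combined protocol and SAP*

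**What the plan says.** All references are to the combined protocol and SAP.

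- **Specific Aim.** The study sets out "To document and compare the procedural and postoperative costs, recovery time, and outcomes of two procedure types", namely robotic-assisted UKA and manual TKA.
- **Endpoints, last bullet.** It opens with "The procedural costs of the different type of knee replacement allocated into different cost centers" and continues: "The charges, costs, and reimbursements will also be examined and the data be gathered from the hospital accounting software".
- **Study Enrollment Procedure.** There is no randomisation: "The patient and surgeon then will determine which prosthesis is most appropriate for their surgical procedure".
- **Cost Data.** Financial data come from each facility's accounting system. There is a fallback: "If data cannot be attained using this method, CPT codes will be recorded and cross-referenced with the 2010 Medicare Fee Schedule". Its justification is that "more than 60% of arthroplasty cases are reimbursed by this agency".
- **Exclusion Criteria.** One payer class is removed: "Patient who is on workmen's compensation". The Endpoints section gives the reason as a possible influence on rehabilitation and recovery, not on payment.
- **Data collected and summarised.** The Time and Events Chart lists demography (not itemised), medical history, medication and coexisting disease. Patient Characteristics names age, height, body surface area, race and gender. Neither names payer or insurance.
- **Data Analysis and General Statistical Considerations.** The analysis is descriptive, with primary presentations pooled over centers. No stratification or covariate adjustment is stated.

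**The concern.** The amount reimbursed for an operation can depend on who pays for it as well as on what was done. The plan's own Medicare figure leaves room for a sizeable minority of other payers, and entry from age 21 to 80 does not confine the sample to one payer's population. Because the procedure is chosen, nothing in the design balances payer between UKA and TKA. A mean reimbursement for each procedure, pooled over payers, is then a weighted average whose weights may differ between the groups.

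What is at stake is the reading of that one item. A UKA–TKA difference in reimbursement could arise with no difference in what any payer pays for the two operations, and without payer on file the two explanations could not be separated afterwards.

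**Working it through.** The plan gives no reimbursement amount, payer share by procedure, sample size or effect size for this item, so there is no figure of its own to reproduce. The check has two parts.

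**1. Does any provision hold payer constant?**

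- The workers' compensation exclusion removes one class. Medicare versus other payers remains.
- The fee-schedule fallback puts records on one payer's rate, but only records for which facility data cannot be obtained. Used for some records, it mixes actual and scheduled amounts.
- Age is summarised by group, but it is at most a partial proxy for payer, and no adjustment for it is planned.
- Homogeneity testing is mentioned under Patient Characteristics, where payer is not among the listed variables.

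None of these closes the gap.

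**2. How large could the effect be?**

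Inputs:

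- From Cost Data: Medicare share of arthroplasty cases above 60%, so up to 40% other. This describes arthroplasty cases in general and is not split by procedure.
- Assumed: Medicare pays 1 and other payers pay k, with k = 1.25, 1.5 or 2.0, the same for both procedures. There is therefore no true procedure difference within payer.
- Assumed: Medicare shares mU (UKA) and mT (TKA), set symmetrically around 60%.

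Mean reimbursement in a group = m + (1 − m)k.

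Apparent difference = [mU + (1 − mU)k] / [mT + (1 − mT)k] − 1.

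| Medicare share, UKA vs TKA | k = 1.25 | k = 1.5 | k = 2.0 |
|---|---|---|---|
| 60% vs 60% | 0% | 0% | 0% |
| 55% vs 65% | +2.3% | +4.3% | +7.4% |
| 50% vs 70% | +4.7% | +8.7% | +15.4% |
| 70% vs 50% | −4.4% | −8.0% | −13.3% |

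For 50% vs 70%: 1.125/1.075 = 1.047; 1.25/1.15 = 1.087; 1.5/1.3 = 1.154. The reversed row inverts these ratios: 1.075/1.125 = 0.956; 1.15/1.25 = 0.920; 1.3/1.5 = 0.867. If k = 1, every cell is 0%.

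**Partial use of the fallback.** Suppose both groups have a 60% Medicare share, 30% of TKA records are priced on the Medicare schedule, and no UKA records are. UKA mean = 0.6 + 0.4k, and TKA mean = 0.7(0.6 + 0.4k) + 0.3.

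- k = 1.25: 1.10/1.07 gives +2.8%.
- k = 1.5: 1.20/1.14 gives +5.3%.
- k = 2.0: 1.40/1.28 gives +9.4%.

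So uneven use of the fallback can itself create a difference, even with identical payer mix.

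**After the fix.** Within a payer class the two means are equal by construction (1 and 1, or k and k). Standardised to a common 60/40 mix, both are 0.6 + 0.4k. The artefact is 0% in every scenario.

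**The case against.** The strongest reply is that reimbursement is a minor item. It appears in no stated objective, and the sentence says it will be examined, whereas several other endpoints are explicitly to be compared. This stands, and it lowers the priority. It does not remove the point: the same bullet is organised by type of knee replacement and the Specific Aim compares the two procedures, so a tabulation by procedure is the natural reading, though an inferred one.

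A reader might go further and infer that the study's cost-effectiveness conclusion, or a margin of payment over cost, is biased. The documents do not support that. They define no margin or payment-to-cost measure, the economic aim is framed in costs, and nothing shows that payer mix distorts resource costs.

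A reader might also infer that payer goes unrecorded. That is too strong. Patient Characteristics lists what will be summarised, not everything collected: employment, salary and operated side are gathered under Endpoints but are absent from that list. Demography is not itemised, and hospital accounting software may well hold payer. What can be said is that no section plans to extract it or use it.

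Finally, the payer ratios and group shares above are assumptions, and the documents do not establish that payment rates differ between payers. This also stands, so the figures are illustrative only.

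**Conclusion.** The point holds in a narrow, conditional form. If payer mix differs between UKA and TKA, and if payers pay different rates, pooled reimbursement by procedure will reflect payer mix as well as procedure, and the plan has no step that would detect or remove this. Both conditions are plausible, because the procedure is chosen and the plan itself acknowledges payers other than Medicare; the documents establish neither.

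Size and direction are unknown. Under the stated assumptions the artefact runs from 0% (equal mix) to between 4.7% and 15.4% in favour of UKA at Medicare shares of 50% vs 70%, and has the opposite sign if the shares are reversed. It would be a mistake to read this as a predicted advantage for UKA. Priority is low to moderate.

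**What to change.** 1. Extract primary payer with each reimbursement record from the hospital accounting system, and tabulate it by procedure.
2. Report reimbursement by procedure within payer class (Medicare, other), or standardise both groups to one stated payer mix.
3. State, by procedure, how many records were priced by the Medicare Fee Schedule fallback, so that actual and scheduled amounts are not silently combined.
4. Label pooled reimbursement by procedure as descriptive and not as evidence of a procedure difference.

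The cost is one extra field in an extract already planned and one extra table. The drawback is smaller cells in the non-Medicare class and so less precise estimates there; standardisation keeps a single summary figure but depends on those same cells.

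### Patient and surgeon choose the procedure, yet the plan names no adjustment for the UKA/TKA comparison; a short prespecified adjusted analysis would be a cheap improvement

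*Combined protocol and SAP*

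**What the plan says.** The Specific Aim is comparative: "To document and compare the procedural and postoperative costs, recovery time, and outcomes of two procedure types", namely robotic-assisted UKA and manual TKA. Medical Need adds that the comparison should help to show whether robotic-assisted surgery is cost-effective. Endpoints calls for comparison by procedure type for length of stay, EQ-5D, durable equipment and return to work.

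The arms are not randomised. Under Study Enrollment Procedure the surgeon sets out the options judged suitable for the individual patient, and then "The patient and surgeon then will determine which prosthesis is most appropriate for their surgical procedure". Only afterwards is the study explained and consent sought.

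Data Analysis lists frequency tables, means, standard deviations and ranges. General Statistical Considerations sets a two-sided 0.05 level for tests and intervals, bases the primary analyses on data pooled across centers, and allows optional center summaries. Patient Characteristics adds demographic summaries by group and homogeneity testing, with no stated consequence if the groups differ.

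Endpoints records which leg was operated on "because this could factor into time it takes to return to driving", but then says only: "The length of time to return to driving will be reported by procedure type".

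On disease extent, the opening background section presents UKA as an alternative to TKA "assuming the patient's osteoarthritis has remained isolated in a single compartment". The introductory paragraph of Inclusion Criteria says that participants "are candidates for partial joint replacement because of pain and joint stiffness". The list under the same heading admits patients "Diagnosed with osteoarthritis in one or more compartments of the knee". Exclusion Criteria removes "Patients receiving an isolated patellofemoral UKA, lateral UKA, or bi-compartmental arthroplasty", so the UKA arm appears to be medial only.

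**The concern.** When surgeon and patient pick the procedure, the features that drive the choice (age, weight, coexisting disease, pre-operative function, work and lifestyle) can also drive cost, recovery and outcome. A raw contrast mixes the two. Pooling across centers adds another route: if centers differ both in their share of UKA and in their recorded costs, part of the cost difference belongs to the center. Cost Data draws on each facility's own accounting system, so such differences are plausible.

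The plan recognises one such factor, operated side, and then does not use it. Since the comparison is meant to inform a cost-effectiveness argument, an unadjusted difference at the 0.05 level could be read as an effect of the procedure when it is partly an effect of selection.

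**Working it through.** **What the plan supplies.** There is no figure to reproduce. The available text gives no sample size, arm ratio, effect size, SD, number of centers or center mix. The only numerical input taken from the plan is the two-sided 0.05 level. Everything else below is assumed, including direction.

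**Does anything in the plan already adjust?**
- *Homogeneity testing* detects imbalance; it does not correct it. Its power against a 0.2 SD imbalance is 16.9% at 50 per arm and 29.3% at 100. Against 0.5 SD it is 70.5% and 94.2%.
- *Optional center summaries* are not a within-center comparison of procedures.
- *Reporting surveys by discharge type* does not adjust for selection: discharge status arises after surgery.
- *Change from the pre-operative score* is unavailable for costs, length of stay, and time to return to work or driving, which have no pre-operative value. The Forgotten Joint Score is scheduled only after surgery.

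**Illustration 1: an outcome with a pre-operative score.** Let the score differ by g SD between arms and correlate r with the outcome, with no procedure effect and n per arm.
- Bias: b = g × r. Standard error: se = √(2/n).
- Rejection rate = 1 − Φ(1.96 − b/se) + Φ(−1.96 − b/se).
- g = 0.4, r = 0.5, n = 100: b = 0.20, se = 0.1414, b/se = 1.414, rate = 0.293.
- g = 0.2, r = 0.5, n = 100: b = 0.10, rate = 0.109.
- At n = 50 these become 0.170 and 0.079. At g = 0 the rate is 0.050.

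Simulation (10,000 runs, n = 100) with regression on the score:

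| Score gap (SD) | Unmeasured gap (SD; correlation 0.3) | Raw | Adjusted |
|---|---|---|---|
| 0 | 0 | 0.052 | 0.050 |
| 0.2 | 0 | 0.102 | 0.048 |
| 0.4 | 0 | 0.294 | 0.049 |
| 0.4 | 0.2 | 0.451 | 0.080 |
| 0.4 | 0.4 | 0.609 | 0.153 |

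The adjusted 5% in the first three rows holds by construction, because the score is the only confounder there. The last two rows show that adjustment reduces the error but does not remove it when something unmeasured also differs.

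**Illustration 2: center and cost.** Take two equal centers, overall UKA share s, and a gap g in UKA share between them. The share of patients from the higher-UKA center then differs between the arms by g/4 × (1/s + 1/(1−s)) = g/(4s(1−s)). If recorded costs are 10–20% higher at one center:
- s = 0.5, g = 0.2: multiplier 0.20, spurious cost difference 2–4%.
- s = 0.5, g = 0.4: multiplier 0.40, difference 4–8%.
- s = 0.2, g = 0.2: multiplier 0.3125, difference 3.1–6.3%.
- g = 0: no difference from this source.

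This sizes a possible bias from center only. It does not quantify what patient-level adjustment would gain for costs.

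**Room for covariates.** Procedure, pre-operative value, age, sex, BMI and coexisting disease make 6 terms. With 2–4 centers (1–3 more) the total is 7–9, or 8–10 with operated side. At an assumed 50 per arm, 100/9 = 11.1 to 100/7 = 14.3 patients per term; for a model with side, 100/10 = 10 to 100/8 = 12.5. The set must stay short.

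**Disease extent.** If the introductory paragraph of Inclusion Criteria governs, all participants are candidates for partial replacement and this imbalance may be absent. If the list governs, TKA patients may have disease that could not have entered the UKA arm. If a share q of TKA patients falls outside the UKA pattern, restricting to the rest multiplies the standard error by √((1 + 1/(1−q))/2) with equal arms: 1.080, 1.225 and 1.581 at q = 0.25, 0.50 and 0.75.

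**The case against.** The plan describes itself as a minimal-risk collection of data. Most objectives are to quantify or report, Data Analysis is descriptive, and no specific test is named for any UKA/TKA endpoint, so the 0.05 level is a general statement. Both arms also share limits on BMI, ligaments, contracture, flexion, alignment, long-acting narcotics, workers' compensation and the contralateral knee, which plausibly shrink any gap. The sizes above are assumed.

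Much of this is fair. It limits how strongly the point can be put, and the plan is silent on adjustment rather than opposed to it. But the Specific Aim and several endpoints are explicitly comparative, and tests and intervals are foreseen. Shared limits narrow the population without balancing the arms inside it.

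A reader might go further and infer that the TKA arm has more extensive disease, so that the comparison favors UKA and the primary analysis must be restricted to matching compartment patterns. The documents do not support that. The introductory paragraph of Inclusion Criteria would make disease extent similar in both arms if it applies to everyone, in which case this source could contribute nothing. Restriction would also change the target population, and overlap in compartments is not overlap in the surgeon's judgement of suitability.

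**Conclusion.** The point holds as an inexpensive improvement. Procedure is chosen, the aim is comparative, and nothing in the plan adjusts for selection or center. This is true under either reading of the eligibility text.

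The bias has no known direction or size. The contrast of about 29% with about 5% rests on 100 per arm, a 0.4 SD score gap, correlation 0.5 and a single measured confounder; with an unmeasured 0.4 SD gap as well, the adjusted rate is 15%. A reader might take these as expected error rates for this study, or carry the gain over to costs, length of stay, or return to work or driving. Neither follows: the inputs are not in the documents, and those endpoints have no pre-operative value to adjust for.

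**What to change.** In Data Analysis:

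1. Make the main UKA/TKA comparison for each endpoint a prespecified regression, with one form named per endpoint type. Adjust for the pre-operative value of the same measure where collected, age, sex, BMI, coexisting disease and center. Add operated side for return to driving.
2. Analyse return to work among patients employed before surgery. Employment mainly defines who can be analysed there.
3. Keep the covariate set short, since the available text gives no sample size. State how missing pre-operative values are handled, because Patient Follow-up makes questionnaire completion permissive.
4. Keep the unadjusted tables as descriptive. Report standardised differences and covariate overlap by arm rather than relying on homogeneity tests.
5. State that residual confounding limits causal conclusions.

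Separately, reconcile the two statements in Inclusion Criteria on partial-replacement candidacy and number of compartments. If TKA patients may have disease that could not have entered the UKA arm, record which compartments are involved and add a sensitivity analysis restricted to patients whose pattern could have entered either arm.

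Cost: analysis wording, a clarification of the eligibility text and a little programming. Demography, coexisting disease, pre-operative scores and radiographs are already in the Time and Events Chart; side and employment are already documented; BMI is needed for eligibility. The sensitivity analysis, if needed, adds one abstracted item and loses some precision. No new patients or visits are required.
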